## 8 Visit schedule and assessments

The below Assessment Schedules ([Table 8-1](#), [Table 8-2](#), [Table 8-3](#), [Table 8-4](#), [Table 8-5](#) and [Table 8-6](#)) list all assessments with an X when they are performed. All data obtained from these assessments must be supported in the participant's source documentation. The "X" in the table denotes the assessments to be recorded in the clinical database or received electronically from a vendor. The "S" in the table denotes the assessments that are only in the participant's source documentation and do not need to be recorded in the clinical database.

Participants should be seen for all visits/assessments as outlined in the assessment schedules or as close to the designated day/time as possible. The Investigator should promote compliance by instructing the participant to attend the study visits as scheduled and by stating that compliance is necessary for the participant's safety and the validity of the study. Missed or rescheduled visits should not lead to automatic discontinuation. The participant should be instructed to contact the Investigator if he/she is unable for any reason to attend a study visit as scheduled or if he/she is unable for any reason to take the study treatment as prescribed.

Participants who prematurely discontinue the study should be scheduled for the End of Study (EOS) visit within 7 days. At this final visit, all the assessments mentioned under EOS visit should be performed, all dispensed investigational product should be reconciled, and the

adverse event and concomitant medications recorded on the CRF. Participants that prematurely discontinue should also have a remote follow-up safety visit performed 30 days after the EOS visit.

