2.4.1.1 Visit windows

Visit windows will be used for data that are summarized by visit; they are based on the study evaluation schedule and comprise a set of days around the nominal visit day. When visit windows are used, all visits, including unscheduled visits, will be re-aligned (i.e., they will be mapped into one of the visit windows). In the case of major deviations from the visit schedule, or due to unscheduled visits, several assessments for a participant may fall in a particular visit window (either scheduled or unscheduled). Approaches for handling multiple assessments in a visit window are outlined below.

The following steps are used to determine the cut-offs for visit windows:

- The visit window associated with the previous assessment ends prior to the middle point; the visit window associated with the latter assessment begins after the middle point. In case the middle point is an exact study day, it will belong to the previous assessment.
- The visit window of the first post-vaccination assessment starts the day after the second dose of the COVID-19 vaccine for Cohorts 1 – 5, and the day after the COVID-19 vaccine booster for Cohort 6, unless otherwise specified.

Tables 2 – 10 provide visit windows for applicable parameters.

Table 2**Cohort 1 visit windows for SARS-CoV-2 qualitative antibody / CD19+ B cells / T cell**

Analysis visit	Nominal time point	Scheduled visit day (target study day)	Visit window (study days)
Pfizer vaccine:			
Pre-vaccination	Day 1	1	≤1
14 days post-vaccination	Day 36	36	(vaccine day + 1) to 64
70 days post-vaccination	Day 92	92	65 to 147
180 days post-vaccination	Day 202	202	148 to 247
270 days post-vaccination	Day 292	292	248 to 337
360 days post-vaccination	Day 382	382	≥338
Moderna vaccine:			
Pre-vaccination	Day 1	1	≤1
14 days post-vaccination	Day 43	43	(vaccine day + 1) to 71
70 days post-vaccination	Day 99	99	72 to 154
180 days post-vaccination	Day 209	209	155 to 254
270 days post-vaccination	Day 299	299	255 to 344
360 days post-vaccination	Day 389	389	≥345

Note:

- Pre-vaccination and study day are derived as outlined in [Section 2.1.1](#).
- Vaccine day is the study day of the second dose of the COVID-19 vaccine.
- Assessments performed between the first and second doses of the COVID-19 vaccine are not assigned an analysis visit.

Table 3**Cohort 1 visit windows for serum immunoglobulin (IgG, IgM)**

Analysis visit	Nominal time point	Scheduled visit day (target study day)	Visit window (study days)

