Pfizer vaccine:			
Pre-vaccination	Day 1	1	≤1
14 days post-vaccination	Day 36	36	(vaccine day + 1) to 64
70 days post-vaccination	Day 92	92	65 to 147
180 days post-vaccination	Day 202	202	148 to 292
360 days post-vaccination	Day 382	382	≥293
Moderna vaccine:			
Pre-vaccination	Day 1	1	≤1
14 days post-vaccination	Day 43	43	(vaccine day + 1) to 71
70 days post-vaccination	Day 99	99	72 to 154
180 days post-vaccination	Day 209	209	155 to 299
360 days post-vaccination	Day 389	389	≥300

Note:

- Pre-vaccination and study day are derived as outlined in [Section 2.1.1](#).
- Vaccine day is the study day of the second dose of the COVID-19 vaccine.
- Assessments performed between the first and second doses of the COVID-19 vaccine are not assigned an analysis visit.

[figure not shown]

Table 5**Cohorts 2 and 3 visit windows for SARS-CoV-2 qualitative antibody / CD19+ B cells (Cohort 2 only) / T cell**

Analysis visit	Nominal time point	Scheduled visit day (target study day)	Visit window (study days)
Pfizer vaccine:			
Pre-vaccination	Day 1	1	≤1
14 days post-vaccination	Day 36	36	(vaccine day + 1) to 119
180 days post-vaccination	Day 202	202	120 to 247
270 days post-vaccination	Day 292	292	248 to 337
360 days post-vaccination	Day 382	382	≥338
Moderna vaccine:			
Pre-vaccination	Day 1	1	≤1
14 days post-vaccination	Day 43	43	(vaccine day + 1) to 126
180 days post-vaccination	Day 209	209	127 to 254
270 days post-vaccination	Day 299	299	255 to 344
360 days post-vaccination	Day 389	389	≥345

Note:

- Pre-vaccination and study day are derived as outlined in [Section 2.1.1](#).
- Vaccine day is the study day of the second dose of the COVID-19 vaccine.
- Assessments performed between the first and second doses of the COVID-19 vaccine are not assigned an analysis visit.

Table 6**Cohorts 2 and 3 visit windows for serum immunoglobulin (IgG, IgM)**

Analysis visit	Nominal time point	Scheduled visit day (target study day)	Visit window (study days)
Pfizer vaccine:			
Pre-vaccination	Day 1	1	≤1
180 days post-vaccination	Day 202	202	(vaccine day + 1) to 292
360 days post-vaccination	Day 382	382	≥293
Moderna vaccine:			
Pre-vaccination	Day 1	1	≤1
180 days post-vaccination	Day 209	209	(vaccine day + 1) to 299
360 days post-vaccination	Day 389	389	≥300

Note:

- Pre-vaccination and study day are derived as outlined in [Section 2.1.1](#).
- Vaccine day is the study day of the second dose of the COVID-19 vaccine.

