 - For *continuous variables*, the assessment with the study day that is closest to the target study day is selected. If two assessments are equidistant from the target study

day, the earlier assessment is selected (if one of the two equidistant assessments is an unscheduled assessment, it should be excluded from consideration).

- For *categorical variables*, the assessment with the worst result is selected.

If categorical variables are based on continuous variables, the analysis visit will be assigned to the continuous variable, and this analysis visit will be used for the derived categorical variable.

In situations where the same assessment is performed more than once on the same date the repeated assessment will be used.

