2.5.1 Primary endpoint(s)

The primary endpoint is achieving immune response as defined by a positive SARS-CoV-2 qualitative IgG antibody assay ≥ 14 days after full course (2 doses) vaccination (yes/no).

The primary estimand is described by the following attributes:

- **Population:** Defined through appropriate inclusion/exclusion criteria to reflect the targeted population. Relapsing MS participants subdivided into 6 cohorts. (1) Will receive a full course (2 doses) of a COVID-19 mRNA vaccine ≥ 2 weeks prior to starting ofatumumab 20 mg s.c. treatment; (2) Will receive a full course (2 doses) of a COVID-19 mRNA vaccine after ≥ 4 weeks of commercial ofatumumab 20 mg s.c. treatment (3) Will receive a full course (2 doses) of a COVID-19 mRNA vaccine after ≥ 4 weeks of interferon or glatiramer acetate treatment (4) Completed a full course (2 doses) of a COVID-19 mRNA vaccine after ≥ 4 weeks of commercial ofatumumab 20 mg s.c. treatment but has not yet received a COVID-19 mRNA booster (5) Completed a full course (2 doses) of a COVID-19 mRNA vaccine after ≥ 4 weeks of interferon or glatiramer acetate (may or may not have received a COVID-19 mRNA booster) (6) Completed a full course (2 doses) of a COVID-19 mRNA vaccine after ≥ 4 weeks of commercial ofatumumab 20 mg s.c. treatment and received an additional booster vaccine ≥ 14 days prior to screening
- **Variable:** Achieving immune response as defined by a positive SARS-CoV-2 qualitative IgG antibody assay ≥ 14 days after full course (2 doses) vaccination (yes/no)
- **Treatment of interest:** Non-live COVID-19 mRNA vaccine either ≥ 2 weeks prior to ofatumumab start or ≥ 4 weeks after ofatumumab start or while on interferon or glatiramer acetate
- **Intercurrent event:** Discontinuation of treatment/study, or death
- **Summary measure:** Proportion of participants achieving immune response

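### The SAP's worst-result rule lets a second, negative antibody sample override a positive Visit 4 sample in Cohorts 1–3: a one-directional flaw, probably of small effect

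*SAP*

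**What the plan says.** SAP 2.4.1.1 places the SARS-CoV-2 qualitative antibody in analysis windows (Tables 2, 5 and 8). "When visit windows are used, all visits, including unscheduled visits, will be re-aligned", so no result is left out for being off schedule. When a post-vaccination window holds several results, a continuous variable takes the one nearest the target day. For a categorical variable, "the assessment with the worst result is selected".

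This is a default that gives way to any other instruction. Two exceptions are written in:
- "In situations where the same assessment is performed more than once on the same date the repeated assessment will be used".
- "If categorical variables are based on continuous variables, the analysis visit will be assigned to the continuous variable", which brings in the nearest-to-target choice.

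The primary window for Cohorts 2 and 3 with the Pfizer vaccine is printed in Table 5 as "vaccine day + 1) to 119". The Moderna window ends on Day 126. In Cohort 1 the windows end on Day 64 (Pfizer) and Day 71 (Moderna).

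SAP 2.5.1 states: "The primary endpoint is achieving immune response as defined by a positive SARS-CoV-2 qualitative IgG antibody assay", at least 14 days after the second dose. SAP 1.1 sets the primary time point at Visit 4 for Cohorts 1–3 and Visit 2 for Cohorts 4–6. On early withdrawal, Protocol 8 says: "Participants who prematurely discontinue the study should be scheduled for the End of Study (EOS) visit within 7 days", with all EOS assessments done.

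**The concern.** A positive/negative assay is categorical, and the natural reading of worst is negative. If the window holds a positive Visit 4 sample and a negative sample from another date, the rule keeps the negative and scores the participant a non-responder. This conflicts with the plan in four ways:

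- The named primary time point is Visit 4, yet another visit's result can replace it.
- SAP 2.5 defines a responder by one positive assay after the full course. It has no rule for discordant results.
- Non-response imputation (SAP 5.1.3.3) is meant for participants with no valid assessment. Here a valid positive would be scored No.
- Immune conversion (SAP 2.6.1) counts a positive at any qualifying time point. A Cohort 1–3 participant could therefore be a converter and a primary non-responder.

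The rule can only lower the response rate, and only in participants with extra samples, who are likely to be early withdrawals. The observed-case supplementary analysis removes imputation but keeps the worst-result choice, so it would not reveal the problem.

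**Working it through.** **1. Window limits reproduce as midpoints of target days.** Cohort 1: (36 + 92)/2 = 64 and (43 + 99)/2 = 71. Cohorts 2–3: (36 + 202)/2 = 119 and (43 + 209)/2 = 126. All match the SAP. With dose 2 on Day 22 (Pfizer), the window is Days 23–64, or 42 days, in Cohort 1 and Days 23–119, or 97 days, in Cohorts 2–3. Moderna, with dose 2 on Day 29, gives the same lengths.

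**2. Early edge.** The window opens the day after dose 2. Its first 13 days fall short of the 14 days that the endpoint requires, so an ineligible early negative could override a qualifying positive.

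**3. Where a second sample can come from.**
- Early EOS: the qualitative antibody is marked at EOS in Protocol Tables 8-1, 8-3 and 8-4. The Table 8-2 row is not visible in the available text. In Cohort 1, Protocol 8.5.2 measures serum IgG 14 days after dose 2 and withdraws participants below 400 mg/dl, which could bring an EOS draw inside the window.
- Unscheduled visits: no readable schedule row lists an antibody test there. If one were done, it would be mapped in.
- Same-date repeats: not affected, because the repeat is used.

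**4. Ofatumumab in Cohort 1.** Doses fall on Days 36, 43, 50 and 64 (Pfizer) or 43, 50, 57 and 71 (Moderna). Protocol 6.3.2 gives treatment after the visit's assessments. The Visit 4 sample therefore precedes the first dose, and a later in-window sample follows at most three. The fourth is nominally due on the window's last day.

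**5. Cohorts 4–6.** The primary window ends on Study Day 1, the day of the first scheduled antibody draw, so there is essentially no second sample. Their later windows follow the same rule; the 180-day window, for example, covers Days 2–247 (Pfizer) or 2–254 (Moderna).

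**6. Cost of one reversal.** With 22 in a cohort group and missing results kept in the denominator, one reversal costs 1/22 = 4.5 points. Example with Clopper-Pearson 95% intervals: 16/22 = 72.7% (49.8–89.3) becomes 15/22 = 68.2% (45.1–86.1).

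**7. How often.** The documents give no rate of second draws. Assume the planned 10% drop-out is uniform from Visit 4 to EOS (Day 36 to 382, or 43 to 389: 346 days) and take the EOS draw as the drop-out day. The share f with an EOS draw in the primary window is:
- Cohort 1: (64 − 36) = 28 days; f = 0.10 × 28/346 = 0.8%.
- Cohorts 2–3: (119 − 36) = 83 days; f = 0.10 × 83/346 = 2.4%.

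Let s be the per-draw chance that a true responder tests positive, and assume independent draws. A single sample scores s and the worst of two scores s², so the loss is f × (s − s²). At s = 0.95, s − s² = 0.0475; at s = 0.90 it is 0.09.

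| | f | Loss, s = 0.95 | Loss, s = 0.90 |
|---|---|---|---|
| Cohort 1 | 0.8% | 0.04 points | 0.07 points |
| Cohorts 2–3 | 2.4% | 0.11 points | 0.22 points |
| All drop-outs inside the window | 10% | 0.5 points | 0.9 points |

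If the second draw were always negative, the loss could not exceed f: 0.8 or 2.4 points under even drop-out.

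**The case against.** The best reply is that the rule may not govern the primary endpoint. SAP 1.1 names Visit 4 or Visit 2, windows are for data summarised by visit, and the primary result is shown by cohort group. A programmer could reasonably take the nominal visit. That stands as an ambiguity, but the SAP gives no other selection rule and windows this assay explicitly.

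Second, the positive/negative call may rest on a measured value, in which case the nearest-to-target rule applies. The protocol summary mentions a qualitative/quantitative assay, and the conversion endpoint uses titers. SAP 5.3 lists no laboratory derivations, but that does not settle how the laboratory makes the call. This remains a condition on the finding.

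Third, choosing the worst result is conservative, like non-response imputation, and a later negative may matter for sustained response. That has some force for the later windows. For the primary endpoint it replaces a valid observation from the intended day. All results are listed, so any reversal could be found.

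A reader might infer more than the documents support: that visits for illness or relapse routinely supply extra antibody samples, or that a sizeable share of responders have two draws. The readable schedules show no antibody test at unscheduled visits, and Protocol 8.5 says no additional tests will be performed. On the EOS route, even a 10% share would need every planned drop-out to fall in the primary window.

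**Conclusion.** The point holds as a minor defect. As written, the SAP's default can turn a positive, on-schedule primary sample into a non-response in Cohorts 1–3, and it never errs the other way. The expected effect on the primary rate is about 0.2 points or less, given even drop-out, independent draws and 90–95% per-draw positivity. Even with every drop-out inside the window the loss is 0.9 points or less at those positivities. The plan's own 95% margin of error is 17.5 to 20.1 points.

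The conclusion assumes that negative is the worst result, that the primary endpoint uses the windowed value, and that the assay is not derived from a measured value. It does not support a claim of material bias, or of an effect on the primary result in Cohorts 4–6. The reason to act is that the selection rule for the primary variable contradicts its definition, and one reversal in a group of 22 moves the reported rate by 4.5 points.

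**What to change.** In SAP 2.4.1.1, exempt the SARS-CoV-2 qualitative antibody from the worst-result rule. For each analysis visit use the scheduled sample; for the primary analysis that is Visit 4 in Cohorts 1–3 and Visit 2 in Cohorts 4–6. If it is missing, use the sample closest to the target day among those at least 14 days after dose 2. Continue to list all results. A cross-reference in SAP 2.5.1 would make clear that this rule defines the primary value.

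The wording should also say how a scheduled sample taken a little early is handled, because Protocol Table 8-1 allows Visit 4 three days before its target.

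The cost is one SAP sentence and a small programming change, with no new data. It should be settled before database lock.

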2.4.2 Prior, concomitant and post therapies

Medications will be coded using the World Health Organization (WHO) Drug Dictionary. The WHO Drug Dictionary version used for reporting the study will be indicated in a footnote on relevant outputs.

Medications will be classified as prior or concomitant as follows:

- Prior medications are defined as medications taken prior to the date of Visit 1 (Screening).
- Concomitant medications are defined as medications taken on or after the date of Visit 1 (Screening).

Medications will be categorized into the above classes based on recorded or imputed start and end dates (see [Section 5.1.3](#)).

Prior and concomitant medications will be summarized with frequency counts and percentages by cohort group, Anatomical Therapeutic Chemical (ATC) class and PT. Tables will show the overall number and percentage of participants receiving at least one medication of a particular ATC class and at least one medication of a particular PT. A separate summary of prior MS DMTs by PT will be provided.

Non-drug therapies/procedures will be coded using MedDRA terminology. The MedDRA version used for reporting the study will be indicated in a footnote on relevant outputs. Non-drug therapies/procedures will be classified as prior or concomitant based on recorded or imputed start and end dates as outlined above for medications.

Prior and concomitant non-drug therapies/procedures will be summarized by cohort group, primary SOC and PT. Tables will show the overall number and percentage of participants with at least one non-drug therapy/procedure of a particular primary SOC and at least one non-drug therapy/procedure of a particular PT.

2.5 Analysis supporting primary objective(s)

The primary objective of this study is to characterize those achieving immune response after receiving a full course (2 doses) vaccination with a non-live mRNA COVID-19 vaccine (Pfizer or Moderna vaccine) in participants treated with ofatumumab 20 mg s.c. once monthly. This will be achieved by estimating the immune response rate using the SAF.

An immune responder is a participant achieving immune response as defined by a positive SARS-CoV-2 qualitative IgG antibody assay after full course (2 doses) vaccination.

2.5.1 Primary endpoint(s)

The primary endpoint is achieving immune response as defined by a positive SARS-CoV-2 qualitative IgG antibody assay ≥ 14 days after full course (2 doses) vaccination (yes/no).

The primary estimand is described by the following attributes:

- **Population:** Defined through appropriate inclusion/exclusion criteria to reflect the targeted population. Relapsing MS participants subdivided into 6 cohorts. (1) Will receive a full course (2 doses) of a COVID-19 mRNA vaccine ≥ 2 weeks prior to starting ofatumumab 20 mg s.c. treatment; (2) Will receive a full course (2 doses) of a COVID-19 mRNA vaccine after ≥ 4 weeks of commercial ofatumumab 20 mg s.c. treatment (3) Will receive a full course (2 doses) of a COVID-19 mRNA vaccine after ≥ 4 weeks of interferon or glatiramer acetate treatment (4) Completed a full course (2 doses) of a COVID-19 mRNA vaccine after ≥ 4 weeks of commercial ofatumumab 20 mg s.c. treatment but has not yet received a COVID-19 mRNA booster (5) Completed a full course (2 doses) of a COVID-19 mRNA vaccine after ≥ 4 weeks of interferon or glatiramer acetate (may or may not have received a COVID-19 mRNA booster) (6) Completed a full course (2 doses) of a COVID-19 mRNA vaccine after ≥ 4 weeks of commercial ofatumumab 20 mg s.c. treatment and received an additional booster vaccine ≥ 14 days prior to screening
- **Variable:** Achieving immune response as defined by a positive SARS-CoV-2 qualitative IgG antibody assay ≥ 14 days after full course (2 doses) vaccination (yes/no)
- **Treatment of interest:** Non-live COVID-19 mRNA vaccine either ≥ 2 weeks prior to ofatumumab start or ≥ 4 weeks after ofatumumab start or while on interferon or glatiramer acetate
- **Intercurrent event:** Discontinuation of treatment/study, or death
- **Summary measure:** Proportion of participants achieving immune response

2.5.2 Statistical hypothesis, model, and method of analysis

The number and percentage of responders will be presented by cohort group and overall. The 2-sided 95% CI for the proportion of responders will be calculated using an exact method ([Clopper and Pearson, 1934](#)).

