## 4 Rationale

### 4.1 Rationale for study design

A multicenter, 6-cohort, open-label, comparator design has been selected in order to render feasible recruitment given the study's expedited schedule based on the importance of this dataset. The study will address two questions:

1. Can participants treated with ofatumumab develop an immune response if receiving a COVID-19 mRNA vaccine two weeks prior to ofatumumab start?
2. If receiving COVID-19 mRNA vaccine after introduction of ofatumumab treatment, can participants develop an immune response?

[figure not shown]
Participant Cohorts 3 and 5 on interferon or glatiramer acetate are included as a comparator.

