## **12 Data analysis and statistical methods**

The analysis will be conducted on all participant data at the time the trial ends. Any data analysis carried out independently by the investigator should be submitted to Novartis prior to publication or presentation.

Categorical variables will be presented as counts and percentages. For continuous variable, mean, standard deviation, minimum, 25th percentile, median, 75th percentile, and maximum will be presented. All summaries will be presented for Cohort 1, Cohorts 2 and 4, Cohorts 3 and 5, and Cohort 6.

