1.1 Study design

This is a 6-cohort, multicenter prospective study in up to 88 participants with relapsing multiple sclerosis (MS). Up to 66 of the participants will begin treatment with ofatumumab or already be on commercial ofatumumab, the remaining 22 participants will remain on interferon or glatiramer acetate.

In this study, participants must intend to receive or have received a full course (2 doses) of a non-live coronavirus 2019 (COVID-19) messenger ribonucleic acid (mRNA) (Pfizer or Moderna) vaccine. Participants also must meet inclusion criteria and not meet exclusion criteria.

The study consists of 2 periods as outlined below.

Screening period

Participants will enter a screening period of up to 7 days to assess eligibility requirements. Participants in Cohorts 1, 2, 4 and 6 without Hepatitis B virus (HBV) and total serum immunoglobulin results within the past 6 months prior to screening will require central labs to be drawn. Participants with HBV and total serum immunoglobulin results within the specified inclusion range the past 6 months prior to screening will not require the labs to be drawn.

Treatment period

Participants will obtain the mRNA vaccine through their HCP (private insurance) or appropriate federal, state or local program. Participants should be instructed to provide documentation of vaccine administration to the Study Doctor at the next scheduled on-site study visit.

Cohort 1: Relapsing MS participants receiving a full course (2 doses) of a non-live COVID-19 mRNA vaccine ≥2 weeks prior to ofatumumab start.

For participants who receive the Pfizer vaccine, the first of three 20 mg subcutaneous (s.c) ofatumumab loading doses will be administered on Day 36 or 2 weeks after receiving a full course (two doses) of a COVID-19 vaccine. The 2nd and 3rd loading doses should be administered on Day 43 and Day 50 or 7 and 14 days respectively after the 1st loading dose. Subsequent dosing includes 20 mg s.c. administered monthly starting at Day 64.

For participants who receive the Moderna vaccine, the first of three 20 mg s.c ofatumumab loading doses will be administered on Day 43 or 2 weeks after receiving a full course (two doses) of a COVID-19 vaccine. The 2nd and 3rd loading doses should be administered on Day 50 and Day 57 or 7 and 14 days respectively after the 1st loading dose. Subsequent dosing includes 20 mg s.c administered monthly starting at Day 71.

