2.1 Data analysis general information

The statistical analysis outlined in this SAP will be performed by [REDACTED], a Novartis-designated Contract Research Organization (CRO), using SAS® version 9.4 or higher.

For continuous variables, descriptive statistics will include number of participants (n), mean, standard deviation, minimum, maximum, median and 25th and 75th percentiles. For categorical variables, frequency counts and percentages will be reported. Where appropriate, 2-sided 95% confidence intervals (CIs) for point estimates of the mean or proportion will be provided.

Unless otherwise stated, all data summaries will be presented by **cohort group** (see below) and on all participants in the respective analysis set.

- Cohort 1
- Cohorts 2 and 4 combined
- Cohorts 3 and 5 combined
- Cohort 6

All data will be listed appropriately.

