2.2 Analysis sets

The Safety Analysis Set (SAF) comprises all participants who signed informed consent and met all entry criteria.

Unless otherwise specified the SAF will be used for all summary tables and listings.

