2.13 Interim analysis

For the purpose of early dissemination of results, an IA will be performed once Cohorts 2 and 4 in combination have ≥ 10 participants enrolled that have had their serum drawn ≥ 14 days after full course (2 doses) vaccination.

A second IA will be performed once Cohort 6 has ≥ 10 participants.

The third IA will be performed once Cohorts 2 – 5 have full enrollment with blood drawn ≥ 14 days after full course (2 doses) vaccination.

The following variables (including but not limited to) will be summarized for each IA mentioned above:

- Disposition
- Demographics

- Baseline characteristics
- Immune response-related variables
- AEs, SAEs and AEs leading to study discontinuation
- Deaths

Since there will be no hypothesis testing involved, statistical adjustment for the IA will not be made at the stage of final analyses.

3 Sample size calculation

The sample size of 20 participants per cohort is selected based on budget and need for early availability of results. This sample size of 20 participants will provide estimates of proportion of responders with margin of error (half-width of a 95% CI) of 20.1%, 19% and 17.5% corresponding to response rates of 70%, 75% and 80%, respectively. Adjusting for 10% drop-out, 22 participants will be enrolled in Cohort 1. In combination, 22 participants will be enrolled in Cohorts 2 and 4. In combination, 22 participants will be enrolled in Cohorts 3 and 5. In Cohort 6, 22 participants will be enrolled.

4 Change to protocol specified analyses

There are no changes to protocol specified analyses.

5 Appendix

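### The SAP's overall responder rate pools comparators and pre-ofatumumab Cohort 1 samples with participants vaccinated on ofatumumab, so it does not answer the ofatumumab question

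*SAP*

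**What the plan says.** SAP 2.5 sets the primary objective as describing immune response "in participants treated with ofatumumab 20 mg s.c. once monthly. This will be achieved by estimating the immune response rate using the SAF". The clinical question in SAP 1.2.1 is likewise about participants who receive ofatumumab.

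For the primary endpoint, SAP 2.5.2 then says "The number and percentage of responders will be presented by cohort group and overall", with a Clopper-Pearson interval. The overall line recurs in SAP 2.5.6 (supplementary), 2.6.2 (secondary) and 2.6.6 (secondary supplementary).

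Nothing limits who enters that line. SAP 2.1 presents summaries by cohort group "and on all participants in the respective analysis set", and SAP 2.2 reads: "The Safety Analysis Set (SAF) comprises all participants who signed informed consent and met all entry criteria". Treatment is not a condition of membership.

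On the participants not on ofatumumab, SAP 1.1 says that "the remaining 22 participants will remain on interferon or glatiramer acetate", and Protocol 4.1 gives their role: "Participant Cohorts 3 and 5 on interferon or glatiramer acetate are included as a comparator".

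Protocol Section 12 names four reporting groups and no total: "All summaries will be presented for Cohort 1, Cohorts 2 and 4, Cohorts 3 and 5, and Cohort 6". SAP Section 4 says: "There are no changes to protocol specified analyses".

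**The concern.** A single pooled percentage in the primary table looks like the answer to the primary question. Here it averages the comparator into the quantity that the comparator is meant to benchmark. It also adds Cohort 1 results obtained before any ofatumumab was given, and it mixes two-dose with boosted participants. Its weights are enrolment targets, which SAP Section 3 says were set by budget and the need for early results, so its value moves with the recruitment mix.

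If vaccination on ofatumumab lowers response, the pooled row shows a higher rate than was seen in the participants of interest, and a reader could take it for the ofatumumab estimate.

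**Working it through.** **The plan's own figure.** SAP Section 3 gives half-widths of 20.1%, 19% and 17.5% for rates of 70%, 75% and 80% with 20 participants. The simple normal formula, 1.96 × √(p(1 - p)/20), gives 20.08%, 18.98% and 17.53%, so the figures reproduce. Precision was planned for each group, not for a pooled row.

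**Who is in the pooled row at the primary time point.** Sizes are from SAP Section 3 and time points from SAP 1.1.

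| Group | Planned n | Status at the primary sample |
|---|---|---|
| Cohort 1 | 22 | Visit 4, before the first ofatumumab dose |
| Cohorts 2+4 | 22 | Vaccinated on ofatumumab |
| Cohorts 3+5 | 22 | Interferon or glatiramer; Cohort 5 may be boosted |
| Cohort 6 | 22 | Vaccinated on ofatumumab, boosted |

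The Cohort 1 entry follows from Protocol 6.3.2: the first loading dose is due at Visit 4, and dosing comes after that visit's assessments. The analysis window in SAP Table 2 runs to Day 64 (Pfizer) or Day 71 (Moderna), so an unscheduled on-drug sample could enter, but Visit 4 is the only scheduled antibody sample in it.

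Participants not vaccinated on ofatumumab: 22 + 22 = 44 of 88 (50%). Of the other 44, 22 are boosted.

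**Formula.** Let E be the mean rate of Cohorts 2+4 and Cohort 6, and R the mean rate of Cohort 1 and Cohorts 3+5. With four groups of 22, the pooled rate is (E + R)/2, so its excess over E is (R - E)/2.

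| E | R | Pooled | Excess over E |
|---|---|---|---|
| 75% | 75% | 75% | 0 |
| 70% | 80% | 75% | +5 points |
| 60% | 95% | 77.5% | +17.5 points |
| 80% | 70% | 75% | -5 points |

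The documents give no rate by exposure, so every row is an assumption. The 70% and 80% values are the ends of the range that the SAP uses to illustrate precision; 60% and 95% are chosen only to show the scale.

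**Effect on the interval.** Suppose 22/44 respond among those vaccinated on ofatumumab (50.0%, exact interval 34.6% to 65.4%) and 42/44 among the rest. The pooled row is 64/88 = 72.7% (62.2% to 81.7%), and the 50% lies outside its interval. With 31/44 (70.5%, 54.8% to 83.2%) and 35/44, the pooled row is 66/88 = 75.0% (64.6% to 83.6%), and the 70.5% lies inside.

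**Removing only the comparators.** Averaging the three ofatumumab groups (n = 66) gives (80 + 70 + 70)/3 = 73.3% when E is 70% and R is 80%, and (95 + 60 + 60)/3 = 71.7% at 60% and 95%. Part of the gap remains, because Cohort 1 is still sampled before ofatumumab.

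**Later visits.** Cohort 1 is then on ofatumumab, so 22 of 88 (25%) are not. If C is the comparator rate and O the mean rate of the three ofatumumab groups, the pooled rate is (3O + C)/4 and its excess over O is (C - O)/4. That is 2.5 points at 70% and 80%, and 8.75 points at 60% and 95%.

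**The case against.** The strongest reply is that the pooled row matches the estimand as written. SAP 1.2.1 and 2.5.1 list all six cohorts under population, name the vaccine as treatment of interest, including when given on interferon or glatiramer, and use the proportion responding as the summary. This stands against any claim that the row corresponds to no estimand. It does not rescue the row, because the same estimand opens with a question about participants who receive ofatumumab. The two attributes conflict, and a pooled rate cannot answer that question.

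A reader might also infer that the row is biased upward as a matter of fact. The documents do not support that. Protocol 1.1 reports a diminished response with another anti-CD20 agent and a preserved response with interferon and glatiramer, which supports the direction, but it gives no rates.

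Other points stand in whole or in part:

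- The four group rates are reported with their own intervals, there is no hypothesis test, and no decision rests on the pooled row. The primary analysis as a whole is not invalid.
- Cohort 1 answers one of the two design questions in Protocol 4.1. The fault is in averaging it with other cohorts, not in enrolling it.
- Mixing boosted and unboosted participants is not peculiar to the pooled row, since Cohorts 3+5 already do so.
- A total adds to the protocol's four groups without altering them, and SAP Section 1 allows for additional analyses. The statement in SAP Section 4 is therefore an undeclared addition rather than a serious contradiction.
- In the booster analysis, the overall line is the only one that summarises the boosted group as a whole, a group that Protocol 12.5 wants segregated. Deleting it there would lose information.

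**Conclusion.** The concern holds in a limited form. The pooling is plain from the text: half of the planned denominator at the primary time point, and a quarter at later visits, does not represent the condition that the objective asks about. The distortion at the primary time point is (R - E)/2 at planned group sizes: nothing if the rates are equal, 5 points at 70% and 80%, 17.5 points at an assumed 60% and 95%, and negative if the comparators and Cohort 1 respond less well. Actual enrolment will change the weights.

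The size and sign are conditional; the mismatch with the clinical question is not. Because the cohort-group rates still answer the objective, this is a correction that should be made to a reported row, not a failure of the primary analysis.

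**What to change.** 1. Delete the overall line from SAP 2.5.2 and 2.6.2, and from the observed-case repeats in 2.5.6 and 2.6.6. Alternatively, replace it with a row limited to participants vaccinated while on ofatumumab, with Cohorts 2+4 and Cohort 6 also shown separately, and Cohort 1 and Cohorts 3+5 kept apart. Defining the row by exposure at vaccination, rather than at sampling, keeps its membership the same across visits.
2. In the booster analyses of SAP 2.5.6 and 2.6.6, keep a total but restrict it to the ofatumumab cohorts, and show boosted comparators separately.
3. List any pooled row that is kept in SAP Section 4 as an addition to Protocol Section 12.

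The cost is SAP wording and a change to table layouts. No new data are needed, and the cohort-group results do not change.
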